## **10. PROTECTION OF HUMAN SUBJECTS**

In this retrospective study, the anonymity of patients is of utmost importance. Several measures are taken to ensure the confidentiality of the collected information. Reviewers, monitors and data analysts are under a confidentiality agreement with the CRO to maintain the secrecy of the

#### PFIZER CONFIDENTIAL

CT24-WI-GL02-RF02 4.0 Non-Interventional Study Protocol Template For Secondary Data Collection Study 01-Jun-2022 Page 19 of 24 information. Study personnel would never contact individual patients or physicians. During the data collection, the records would never be left unattended and will always be stored in a locked room. Approval from the institutional review board and ethics committee, the custodians of patient data privacy, will be obtained.

Patient identifiers will be kept in a dataset separately from the primary database.

# **10.1. PATIENT INFORMATION**

- All parties will comply with all applicable laws, including laws regarding the implementation of organizational and technical measures to ensure the protection of patient personal data. Such measures will include omitting patient names or other directly identifiable data in any reports, publications, or other disclosures, except where required by applicable laws.
- The personal data will be stored at the study site in e-CRF excel form and will be password
  protected or secured in a locked room to ensure that only authorized study staff has access.
  The study site will implement appropriate technical and organizational measures to ensure that
  personal data can be recovered in the event of a disaster. In the event of a potential personal
  data breach, the study site shall be responsible for determining whether a personal data breach
  has occurred and, if so, providing breach notifications as required by law.
- To protect the rights and freedoms of natural persons concerning the processing of personal data, when study data are compiled for transfer to Pfizer and other authorized parties, patient names will be removed and will be replaced by a single, specific, numerical code, based on a numbering system defined by Pfizer. All other identifiable data transferred to Pfizer or other authorized parties will be identified by this single, patient-specific code. The investigator site will maintain a confidential list of patients who participated in the study, linking each patient's numerical code to his or her actual identity. In case of data transfer, Pfizer will maintain high standards of confidentiality and protection of patients' personal data consistent with the clinical study agreement and applicable privacy laws.

#### 10.2. Institutional review board (IRB)/Independent ethics committee (IEC)

There must be prospective approval of the study protocol, protocol amendments, and other relevant documents (e.g., informed consent forms if applicable) from the relevant IRBs/IECs. All correspondence with the IRB/IEC must be retained. Copies of IRB/IEC approvals must be forwarded to Pfizer.

IRBs/IEC review and approval for each site will be obtained for access to anonymized patient medical records.

#### 10.3. Ethical conduct of the study

The study will be performed following ethical principles that are consistent with the Declaration of Helsinki, ICH GCP, ICMR, and the applicable legislations. The Investigator will perform the study in accordance with the regulations and guidelines governing medical practice and ethics in the country

#### PFIZER CONFIDENTIAL

CT24-WI-GL02-RF02 4.0 Non-Interventional Study Protocol Template For Secondary Data Collection Study 01-Jun-2022 Page 20 of 24 of the study and in accordance with currently acceptable techniques and know-how and in accordance to the below mentioned guidelines.

- 1. Guidelines for Good Pharmacoepidemiology Practices (GPP). Public Policy Committee, International Society of Pharmacoepidemiology. Pharmacoepidemiology and Drug Safety
- 2. Good Practices for Outcomes Research issued by the International Society for Pharmacoeconomics and Outcomes Research (ISPOR)
- 3. Good practices for real-world data studies of treatment and/or comparative effectiveness: Recommendations from the joint ISPOR-ISPE Special Task Force on real-world evidence in health care decision making
- 4. European Medicines Agency (EMA) European Network of Centres for Pharmacoepidemiology and Pharmacovigilance (ENCePP) Guide on Methodological Standards in Pharmacoepidemiology
- 5. FDA Guidance for Industry and FDA Staff: Best Practices for Conducting and Reporting Pharmacoepidemiologic Safety Studies Using Electronic Healthcare Data

# 11. MANAGEMENT AND REPORTING OF ADVERSE EVENTS/ADVERSE REACTIONS

- All AEs will be captured from the medical records.
- Number of Participants Who Experienced a Documented Diagnosis of Veno-occlusive Disease (VOD)/Sinusoidal Obstruction Syndrome (SOS) Post InO Treatment.
- Number of Participants Who Survived Following Treatment For Documented Diagnoses of Venoocclusive Disease (VOD)/Sinusoidal Obstruction Syndrome (SOS).
- Number of Participants With Interrupted InO Treatment Due to VOD/SOS.
- Number of Participants Who Experienced Grade 3 and Grade 4 (Lung/Cardiac/Kidney/Liver) Treatment-Related Adverse Event (TRAE) Following InO initiation.
- All hematological AEs: Neutropenia, febrile neutropenia, and thrombocytopenia
- Being NIS secondary data collection— This study involves retrospective patients treated with InO for R/RB-cell ALL data that exist as unstructured data by the time of study start or a combination of existing unstructured data, which will be converted to structured form during the implementation of the protocol solely in an excel using CRF template.
- It is not possible to link (ie, identify a potential association between) a particular product and medical event for any individual. Thus, the minimum criteria for reporting an AE (ie, identifiable patient, identifiable reporter, a suspect product, and event) cannot be met.

# **12. SAFETY REPORTING**

- This study protocol requires human review of patient-level unstructured data; unstructured data refer to verbatim medical data, including text-based descriptions and visual depictions of medical information, such as medical records, images of physician notes, neurological scans, x-rays, or narrative fields in a database. The reviewer is obligated to report AEs with explicit attribution to any Pfizer drug that appear in the reviewed information (defined per the patient population and study period specified in the protocol). Explicit attribution is not inferred by a temporal relationship between drug administration and an AE but must be based on a definite statement of causality by a healthcare provider linking drug administration to the AE.
- The requirements for reporting safety events on the NIS adverse event monitoring (AEM) Report Form to Pfizer Safety are as follows:
  - All serious and non-serious AEs with explicit attribution to any Pfizer drug that appear in the reviewed information must be recorded on the case report form & AE reporting form and reported, within 24 hours of awareness, to Pfizer Safety using the NIS AEM Report Form.
  - Scenarios involving drug exposure, including exposure during pregnancy, exposure during breast feeding, medication error, overdose, misuse, extravasation, lack of efficacy, and occupational exposure associated with the use of a Pfizer product must be reported, within 24 hours of awareness, to Pfizer Safety using the NIS AEM Report Form.
  - For exposure during pregnancy in studies of pregnant women, data on the exposure to InO during pregnancy, are not reportable unless associated with serious or non-serious adverse events.
  - For these AEs with an explicit attribution or scenarios involving exposure to a Pfizer product, the safety information identified in the unstructured data reviewed is captured in the Event Narrative section of the report form, and constitutes all clinical information known regarding these AEs. No follow-up on related AEs will be conducted.

"All the demographic fields on the NIS AEM Report Form may not necessarily be completed, as the form designates, since not all elements will be available due to privacy concerns with the use of secondary data sources. While not all demographic fields will be completed, at the very least, at least one patient identifier (eg, gender, age as captured in the narrative field of the form) will be reported on the NIS AEM Report Form, thus allowing the report to be considered a valid one in accordance with pharmacovigilance legislation. All identifiers will be limited to generalities, such as the statement "A 35-year-old female..." Other identifiers will have been removed.

• All research staff members must complete the following Pfizer training requirements:

#### "Your Reporting Responsibilities (YRR) Training for Vendors."

These trainings must be completed by research staff members prior to the start of data collection. All trainings include a "Confirmation of Training Certificate" (for signature by the trainee) as a record of completion of the training, which must be kept in a retrievable format. Copies of all signed training certificates must be provided to Pfizer.

# 13. PLANS FOR DISSEMINATING AND COMMUNICATING STUDY RESULTS

In the event of any prohibition or restriction imposed (eg, clinical hold) by an applicable competent authority in any area of the world, or if the investigator is aware of any new information which might influence the evaluation of the benefits and risks of a Pfizer product, Pfizer should be informed immediately.

## 14. ANNEX 1. LIST OF STAND ALONE DOCUMENTS

None

### RE: Protocol Administrative Changes and Clarifications for Study B1931043: A Retrospective analysis of Inotuzumab ozogamicin usage in adult patients with relapsed/refractory (R/R) B-cell Acute Lymphoblastic leukemia (ALL)

Dear Healthcare Provider/Investigator,

This Protocol Administrative Change Letter (PACL) is to notify you of the following administrative changes and clarifications to the B1931043 protocol Version 1 and Version date 14 Nov 2022. The edit described below clarify inconsistencies in the text of the protocol and provide administrative changes. The planned changes is not considered substantial by Pfizer Inc because there is no significant impact to the safety or physical or mental integrity of the study participants, the scientific value of the study, the conduct or management of the study, and therefore *are* not part of a formal amendment.

No.	Serial numbers as per Protocol	Rationale for the changes	Updated details
1	4. RESPONSIBLE PARTIES Principal Investigator(s) of the Protocol	3 sites were withdrawn from the study	Deletion of the following investigators PPD
2	4. RESPONSIBLE PARTIES Principal Investigator(s) of the Protocol	1 site was added to the study	PPD

#### This PACL makes the following changes:

	izer		
3	6. MILESTONES	Change in Milestones- Planned Date	Start of data collection - 13 February 2023 End of data collection - 05 July 2023 Final Study report - 10 October 2023
4	9. RESEARCH METHODS 9.3 Study size	Sample size changed to 32 subjects	Sample size is changed to 32 subjects
5	11. MANAGEMENT AND REPORTING OF ADVERSE EVENTS/ADVERSE REACTIONS 12. SAFETY REPORTING	To clarify the adverse event reporting requirements for structured and unstructured data components. Also, to correct the inconsistency with the protocol template language.	The last 2 paragraphs of Section 11 should be moved to the beginning of Section 12, Adding a subheading "12.1 Structured Data Analysis", under which the 2 paragraphs are pasted and revised. In addition, add a second sub- heading "12.2 Human Review of Unstructured Data" above the original content of Section 12.

In the event that this protocol requires substantial changes that apply globally to all sites in the future or regulatory authorities request that these changes be incorporated into an updated protocol, the administrative changes described in this letter will be incorporated into the amended protocol.

Please inform your institutional review board/ ethics committee of these changes, as required.

Sincerely, [name]

cc: NI study master file

# 1 AMENDMENTS FROM PREVIOUS VERSION(S) None

# **2** INTRODUCTION

*B-cell acute lymphoblastic leukemia (ALL) is a malignant transformation and proliferation of lymphoid progenitor cells in the bone marrow, blood, and extramedullary sites. Only 20% of ALL occurs in adult patients.i Incidence data on adult B-cell ALL in India is lacking.ii The regimens used for pediatric patients with B-cell ALL are mostly used for the treatment of adult patients with B-cell ALL. The treatment of B-cell ALL in adults is mostly based on regimens developed for pediatric patients.* 

Most chemotherapy regimens used to treat adults with B-cell ALL in India consists of multiagent induction, intensification or consolidation, and maintenance phases, together with central nervous system (CNS) prophylaxis using intrathecal chemotherapy, with or without cranial irradiation. Commonly used cytotoxic agents in first line treatment protocol for adult patients with B-cell ALL are cyclophosphamide, vincristine, daunorubicin, L-asparaginase and prednisolone. The prognosis of R/R B-cell ALL has historically been dismal with complete remission (CR) rates of 20-40%, median Overall Survival (OS) of 6 months, and cure rates of <10% even with intensive salvage chemotherapy and haematopoietic stem cell transplantation.iii

Relapsed/Refractory B-cell ALL in adults is a challenging disease, with high mortality resulting from refractory disease or toxicity from intensive chemotherapy regimens. The only curative option in this subset of patients is CR after salvage therapy followed by Allogeneic hematopoietic cell transplantation (Allo-HCT). Even salvage regimens in case of relapse are mostly composed of old agents used in first-line protocols. Although second remissions are possible, with these salvage regimes, these are of short duration unless an allogeneic stem cell transplant is feasible.iv The data on the outcomes of salvage therapy in adult patients with Bcell ALL is lacking from India. However, novel therapies such as Ino have improved the outcomes of this subset of patients, with more patients experiencing CR and minimal residual disease negativity, thus becoming eligible for allo-HCT. The real-world data on the use of Ino monotherapy in cases of adult R/R B cell ALL is limited in Indian settings with knowledge gaps relating to diagnostic and treatment practices. Currently, only a single study is available with Cancer of unknown primary (CUP) data from 8 patients.

InO is an antibody-drug conjugate consisting of a recombinant, humanized IgG4 antibody (G544) covalently bound to a semi synthetic derivative of calicheamicin. Calicheamicin, a cytotoxic natural product produced by microbial fermentation that is significantly more potent than conventional cytotoxic chemotherapeutic agents, binds to the DNA minor groove and causes cell death by inducing double strand DNA breaks. The targeting agent in InO, (G544)

specifically recognizes human CD22, which is expressed on the malignant cells of the majority of B-lymphocyte malignancies, including on the surface of blasts in >90% of patients with B cell ALL.v In 2017, the United States (US) Food and Drug Administration (FDA) and European Medicines Agency (EMA) approved InO for the treatment of adult with R/R B-cell precursor B-cell ALL.vi,vii

# Inotuzumab: mode of action and literature evidence

*ALL* is the second most common acute leukemia in adults. The characteristic features are chromosomal abnormalities and genetic alterations involved in differentiation and proliferation of lymphoid precursor cells. The backbone of therapy remains multi-agent chemotherapy with vincristine, corticosteroids and an anthracycline with allogeneic stem cell transplantation for eligible candidates.viii

The advent of monoclonal antibody (moAb) targeting CD22 (InO) and CD19 (blinatumomab), have dramatically improved the outcome of adults with R/R B cell ALL. These have shown significant survival benefits against standard therapies and expanded the armamentarium of ALL.ix

InO is an anti-CD22 moAb conjugated to the cytotoxic antibiotic calicheamicin. Based on promising phase I/II data, InO was compared to standard salvage chemotherapy in Phase 3 multicenter trial rINO-VATE) of 218 adult patients with CD22+ B cell ALL. The overall response and Minimal residual disease (MRD) negativity rates among responders were significantly higher with InO compared with chemotherapy (81% versus 29%, p < 0.001, and 78% versus 28%, p < 0.001, respectively). More patients who received InO were able to undergo HSCT (41% versus 11%; p < 0.001). The median remission duration and progression-free survival were significantly longer with InO (4.6 versus 3.1 months; p = 0.03, and 5.0 versus 1.8 months; p < 0.001, respectively). The median OS was 7.7 versus 6.7 months (p = 0.04). This was later confirmed with longer follow-up on 326 patients showing 2-year OS rates of 23% versus 10% (p = 0.01) in favor of InO [24]. Predictors for better survival included achievement of CR, MRD negativity, and consolidative HSCT. Patients who achieved MRD negativity derived more benefits regardless of the number of prior therapies.x

InO is an antibody drug conjugates (ADC) comprising of a moAb targeting CD22,xi a cell surface antigen expressed on approximately 90% of B-cell malignancies,xii linked to a cytotoxic agent.

*CD22* is an important modulator of *B*-cell lymphocyte function and survival,xiii and is expressed on mature *B*-cells, which may allow for targeted delivery of the cytotoxic agent.xiv

When InO binds to the CD22 antigen on malignant B-cells, it is absorbed into the cell, at which point the cytotoxic agent calicheamicin is released to destroy the cell.xv

Adding an ADC targeting CD22, such as InO, to existing treatments options, may provide additional anti-tumor activity.xvi

# 2.1 STUDY DESIGN

The study is classified as a Non-interventional study (NIS) secondary data collectionunstructured review with sites/investigators.

R/R B-cell ALL patients who are  $\geq 18$  years old at the time of InO initiation and those who received the drug outside of clinical trials will be evaluated.

Data will be collected retrospectively from patients hospital medical records (paper-based) by members of the direct care team (investigators). We intend to have 7-10 sites across India using InO monotherapy including patients with both private purchase and compassionate use to reach a cohort of approximately 55 patients. If needed, more sites will be enrolled to meet the target cohort. Data will be reviewed and analyzed from all the sites.

Medical records will be reviewed to collect demographic, patient-related, disease-related, and clinical outcome data. These patients will be evaluated for response (CR/CRi), MRD status, duration of remission (DOR), dosage patterns, rate of transplant, survival time for all patients including survival rate at 6 months and 12 months in transplanted patients & non transplanted patients, Relapse free survival (RFS) time, Rate of veno-occlusive disease (VOD) (total during study treatment and post HSCT if any patient underwent HSCT), safety/tolerability, Other adverse effects (including hematological toxicities and raised liver enzymes), Number of cycles to achieve MRD negativity in responders & CR/CRi in Extramedullary disease / lymphoblastic lymphoma (EMD/LBL).

# **Study population**

This is a descriptive study and there is no prior hypothesis specified, therefore a formal sample size calculation is not required. The sample size of approximately 55 patients has been based on the number of patients expected to be available at these 7-10 sites that individually treated the largest number of patients with InO.

The study will include information on approximately 55 patients as per the availability of data from 7-10 sites.

# Data source

Data for this study will be collected through retrospective data collection from 7-10 sites for patients in India who received Inotuzumab for the indication of adult R/R B Cell ALL between

the time period Feb'2017 – Feb'2022. Additional centers may be added at a later stage if the target sample size is not achieved.

Data will be collected in anonymized form on Paper/excel based CRF for the study. Participants will be identified in all study records by a unique participant identification number to allow data management queries to be resolved with reference to source medical records while preserving patient confidentiality.

Medical records will be reviewed from secondary data sources to collect demographic, patientrelated, disease-related, and clinical outcome data & Adverse Event's. These patients will be evaluated for response, duration of response (DOR), survival time from the time of InO initiation till the death or the time data will be retrieved.

Data to be verified in accordance with protocol standards. Before obtaining the data from the selected sites across the nation, the necessary regulatory approval will be ensured.

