# **3. KEY DEFINITIONS**

Index date: The date of initiation of the first cycle of InO.

**Baseline period**: Period from 6 months before index date to the index date. The closest observation recorded during the baseline period and closest to index date will be used as baseline data (when more than one observations are available).

**CR/CRi rate**: Number of patients who achieve complete remission/complete remission with incomplete hematologic recovery (CR/Cri) divided by the total number of patients completing treatment with InO (defined as patients with a recorded date of discontinuation of InO).

**Complete remission (CR)**: is defined as 5% bone marrow blasts, no evidence of disease in the bone marrow, and recovery of peripheral blood count (platelet count of >  $100 \times 109/L$  and absolute neutrophil count of >  $1 \times 109/L$ ).

**CR with incomplete count recovery (CRi)**: is defined as 5% bone marrow blasts and no evidence of disease in the bone marrow, but with incomplete recovery of peripheral blood count. Minimal residual disease (MRD) will be assessed at each participating institution by multicolor flow cytometry.

**MRD negativity r**ate: Proportion of patients in whom minimal residual disease (MRD)-negative status is observed, among patients in whom MRD negativity status has been assessed, at any time until the end of treatment with InO (defined as the date of recorded discontinuation of InO). OS: Time from index date to death.

**RFS:** Time from index date to the earliest date of the following events: death, progressive disease (including objective progression, relapse from CR/CRi, treatment discontinuation due to global deterioration of health status), or the start of new induction therapy or posttherapy haematopoietic stem cell transplantation (HSCT) without achieving CR/CRi.

**EMD**: Extramedullary disease is the presence of leukemic cell aggregates in the form of solid tumor outside that of bone marrow.i

LBL: lymphoblastic lymphoma, is a clonal hematopoietic stem cell disorder of B or T cell originii

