#### 9.7. Limitations of the research methods

- The medical records may not be available for each & every data points provided in the CRF, from the aspect of the clinician or the patient.
- Patients may be lost to follow-up due to the occurrence of AEs, lack of efficacy or other reasons.
- This could be due to censoring events, that is, information on time to outcome event may not available for all study participants. Patient/s in such cases will be marked as "censored" when such information on time to event is not available due to loss to follow-up or non-occurrence of outcome events before the end of the study.
- For such patients (censored because of lost to follow-up due to the occurrence of AEs, lack of efficacy or other reasons), the use of Kaplan-Meier curves will be obtained as estimates of median OS, RFS and time to CR/Cri taking into account patients' attrition.
- The interpretation of data collected retrospectively will be dependent on the completeness and quality of the medical records and the reliability of the abstraction of data from the medical records. However, Source data verification (SDV) will be employed to identify and correct abstraction errors.

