# 5.1 EFFICACY/EFFECTIVENESS ENDPOINT(S)

The primary outcomes of interest are CR/CRi achieved or not following InO treatment which will be measured by binary response and duration of remission which will be measured by time to achieve CR/Cri from InO therapy starts. Other secondary outcomes will be measured by binary response mostly, but time to event for dealth and relapse will be measured by time from starting of the therapy to the event of interest. The longest time from initiation of InO to date of data extracted will be considered as study period. The number of salvage therapies received prior to the InO therapy initiation will be classified into 0, 1 and >1.

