# 6 HANDLING OF MISSING VALUES

Owing to the descriptive nature of the study, analysis will be on available data only. No imputation of missing data will be implemented.

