# 7 STATISTICAL METHODOLOGY AND STATISTICAL ANALYSES

# 7.1 STATISTICAL METHODS

Means, medians, and standard deviations will be provided for continuous variables when performing descriptive analysis of continuous data. Numbers and percentages will be provided for dichotomous and polychotomous variables when performing descriptive analysis of categorical data. The proportion of CR/CRi achieved will be compared across the number of salvage therapies prior to InO initiation with respective 95% confidence interval. Kaplan-Meier survival curve will be drawn for longest time from initiation of InO to date of data extracted. Similarly survival curve will be drawn for relaspse free survival. Median survival or restricted mean survival time will be reported across the number of salvage therapies.

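### The SAP ends survival time only at death or data retrieval; applied literally, patients lost to follow-up without a recorded death would count as survivors to 2023, contrary to the protocol's censoring for loss

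*SAP*

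**What the plan says.** **SAP.** The Data source paragraph of section 2.1 says patients will be evaluated for "survival time from the time of InO initiation till the death or the time data will be retrieved". Section 5.1 adds: "The longest time from initiation of InO to date of data extracted will be considered as study period". Section 7.1 says: "Kaplan-Meier survival curve will be drawn for longest time from initiation of InO to date of data extracted", and that the relapse-free survival curve will be drawn in a similar way. The SAP contains no censoring rule. Section 6 limits the analysis to available data and says "No imputation of missing data will be implemented". The appendices for endpoint definitions and for further statistical methods are both marked as empty.

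**Protocol.** Section 3 defines OS as "Time from index date to death", with no censoring date. Section 9.7 expects some patients to be lost because of adverse events, lack of efficacy or other reasons. It marks a patient as censored when "information on time to event is not available due to loss to follow-up or non-occurrence of outcome events before the end of the study", and it promises Kaplan-Meier "estimates of median OS, RFS and time to CR/Cri taking into account patients' attrition". It does not say at which date a lost patient is censored. Section 9.2 has a third version, in which OS is followed from InO initiation to 6 months or 1 year.

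**The concern.** The SAP offers two ends for the survival clock: a death, or the day the chart is abstracted. A patient who stopped attending and has no death entry fits neither properly. If the sentence is followed as written, that patient's time runs to the retrieval date without an event, although nobody observed the patient alive for most of it. Kaplan-Meier then keeps the patient in the risk set, and the attrition that Protocol 9.7 says will be taken into account disappears.

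The error goes in one direction: survival is overstated. It arises even when loss is unrelated to prognosis, so it is distinct from informative censoring. The outputs exposed are the 6- and 12-month survival rates (Protocol 9.1.4; SAP section 5, Secondary endpoints), median and restricted mean OS (SAP 7.1, 7.2 and 7.2.2) and the tail of the OS curve. If the wording in SAP 7.1 carries the same clock over to RFS, restricted RFS is exposed too. That step is an inference, because the Data source sentence itself covers survival time only.

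**Working it through.** The plan states no survival assumption, event count or loss rate, so there is no figure of its own to reproduce. The check has two parts.

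**1. Time from InO start to retrieval**

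Inputs: InO initiation Feb 2017 to Feb 2022 (Protocol 9.1.1); data collection 13 February to 5 July 2023 (Protocol Administrative Change Letter, item 3).

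- Shortest: 28 Feb 2022 to 13 Feb 2023 = 350 days; 350 / 30.4375 = 11.5 months.
- Longest: 1 Feb 2017 to 5 Jul 2023 = 2,345 days; 2,345 / 30.4375 = 77.0 months.

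This is total time from initiation and includes whatever follow-up was really observed. Since the minimum is just under 12 months, nearly every patient lost in year 1 without a recorded death would count as a 12-month survivor.

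**2. Illustrative effect on OS**

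From the documents: median OS 7.7 months (InO arm of the cited phase 3 trial, Protocol section 7); N = 32 (Administrative Change Letter, item 4).

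Assumed: exponential survival; exponential loss unrelated to prognosis, with share L lost by month 12 in the absence of death; no death captured after loss.

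- Death hazard: λ = ln 2 / 7.7 = 0.0900 per month.
- Loss hazard: c = −ln(1 − L) / 12 = 0.0088, 0.0186, 0.0297 for L = 10, 20, 30%.
- True survival: exp(−λt), which is 58.3% at 6 months, 34.0% at 12 and 11.5% at 24.
- Apparent survival when lost patients are carried to retrieval: S(t) = 1 − [λ/(λ+c)] × [1 − exp(−(λ+c)t)].
- Apparent median: −ln(1 − 0.5(λ+c)/λ) / (λ+c).
- Expected number lost alive before month 12: 32 × [c/(λ+c)] × [1 − exp(−12(λ+c))].

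For L = 20%: λ/(λ+c) = 0.829 and exp(−12(λ+c)) = 0.340 × 0.8 = 0.272, so S(12) = 1 − 0.829 × 0.728 = 0.396.

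| Lost by month 12 | 6-month OS | 12-month OS | 24-month OS | Median (months) | Lost alive before month 12, of 32 |
|---|---|---|---|---|---|
| 0% (true) | 58% | 34.0% | 11.5% | 7.7 | 0 |
| 10% | 59% | 36.7% | 17% | 8.05 | 2.0 |
| 20% | 60% | 39.6% | 23% | 8.51 | 4.0 |
| 30% | 61% | 42.7% | 29% | 9.14 | 6.1 |

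A simulation of 400,000 patients, with time from initiation to retrieval uniform from 11.9 to 76 months, agrees to within rounding. In the same simulation, censoring at last contact returns the true values at every loss rate.

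With the 6-month historical median that Protocol section 7 cites, 12-month OS moves from 25% to 28, 31 and 34% for the same three loss rates.

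For scale, the approximate 95% half-width for 34% survival in 32 patients is 1.96 × √(0.34 × 0.66 / 32) = 16 percentage points.

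**The case against.** The best defence is that the SAP never says that patients of unknown status are counted alive. The Data source sentence can be read as saying how far records are reviewed, section 5.1 as naming the study period, and section 7.1 as saying how far the curve is drawn. Nothing in the SAP revokes Protocol 9.7, and a plan that uses available data only and bars imputation sits poorly with crediting unobserved survival. Death, an administrative end and censoring for loss can coexist.

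Much of this stands. A reader might infer that lost patients are definitely treated as alive until 2023; the documents do not say so, and the consequence follows only from literal application. A reader might also infer that the protocol prescribes censoring at last contact. It does not: it says such patients are censored and leaves the date open. Nor is 11.5 to 77 months the unearned credit per patient, since it includes observed follow-up. If the 6-month or 1-year window of Protocol 9.2 governs, the long-term tail drops out and only the 6- and 12-month figures matter.

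The amount of unknown vital status is also not given. Protocol section 10 rules out contact with patients by study personnel. But abstraction is by the treating team (Protocol 9.1), and Protocol 9.1.2 expects the data needed for the endpoints to be available.

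The defence does not remove the defect. The SAP gives an explicit end point, repeats the extraction date in two further sections, and never mentions loss. The protocol text that would correct it sits in a limitations section and names no date. Two careful analysts could draw different curves from the same charts.

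**Conclusion.** The SAP text is wrong as written. Followed literally, it counts patients lost without a recorded death as survivors to retrieval. That conflicts with Protocol 9.7 and differs from Protocol 9.2.

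Under the stated assumptions, 12-month OS is overstated by about 3, 6 or 9 percentage points (36.7, 39.6 or 42.7% against 34.0%) and the median by about 0.4, 0.8 or 1.4 months. These sizes rest on an assumed loss rate and on no later death being captured. The bias is zero if vital status at retrieval is known for every patient. At 32 patients these shifts are smaller than the sampling half-width, but they are systematic and all favourable.

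This should be fixed before analysis. It does not threaten the study's main result: the survival endpoints are secondary, the study is descriptive, and the CR/CRi rate does not depend on this clock. A reader might infer that the whole efficacy analysis is compromised; the documents do not support that.

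**What to change.** - In SAP 2.1, 5.1 and 7.1, define OS as index date to death, with patients not known to have died censored at the date last documented alive.
- Use data retrieval only as the administrative cut-off, for patients documented alive at that point.
- Give RFS a parallel rule: patients without an event are censored at the last documented disease assessment.
- Make sure both dates are abstracted on the CRF.
- Report the number of patients lost before 6 and before 12 months.
- Reconcile Protocol 9.2 (6-month or 1-year window) and Protocol 9.7 (censoring for loss, date unnamed) with the SAP's Data source paragraph.

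Because Protocol 9.7 expects some loss for lack of efficacy, censoring at the last date alive may still be informative. The report should say so, and a sensitivity analysis would be reasonable.

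Cost: SAP wording and possibly two extra abstracted dates. The CRF is not among the documents, so whether it already holds them is unknown. If it does not, it is cheaper to add them now than to return to the charts later. Reported follow-up will be shorter and survival somewhat less favourable.
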